	Subgroup	Repeat the primary analysis for this endpoint within each of the following subgroups: 
 Actual baseline ordinal score Baseline steroid use Baseline use of emerging COVID-19 treatments Duration of symptoms prior to enrollment (only using the \leq Median; $>$ Median classification)
9. Incidence of new invasive ECMO use through study Day 29 for subjects with baseline clinical status of 5 or 6;	Primary	
 No covariate adjustment
10. Days a subject who has a baseline clinical status of 5 or 6 has a clinical status > 6 up to and including Study Day 29;	Primary	
 No covariate adjustment
	Subgroup	Repeat the primary analysis for this endpoint within each of the following subgroups: 
 Actual baseline ordinal score Baseline steroid use Baseline use of emerging COVID-19 treatment Duration of symptoms prior to enrollment (only using the \leq Median; $>$ Median classification)
11. Proportion of subjects alive and without respiratory failure at Study Day 29;	Primary	
 No covariate adjustment
12. Time (days) to death or ventilation up to and Including Day 29	Primary	Adjust for the following covariates: 
 Baseline dexamethasone use Actual baseline ordinal score Baseline CRP value (Continuous) Age (continuous)

Endpoint	Analysis	Covariates/Subgroups
13. Days of hospitalization from date of admission by Study Day 29.	Primary	
 No covariate adjustment for this analysis
	Subgroup	Repeat the primary analysis for this endpoint within each of the following subgroups: 
 Actual baseline ordinal score Baseline steroid use Baseline use of emerging COVID-19 treatment Duration of symptoms prior to enrollment (only using the <= Median; > Median classification)
Other Secondary Endpoints: Safety		
1. Values of CRP ferritin, D-dimer, LDH, and fibrinogen on Study Day 1: Study Days 3, 5, 8, 11,15 and 29	Primary	
 No covariate adjustment
2. 14-day Mortality	Primary	1. Adjust for the following covariates: 
 Actual baseline ordinal score Baseline steroid use
3. 28-day Mortality	Primary	1. Adjust for the following covariates: 
 Actual baseline ordinal score Baseline steroid use

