Primary	Ordinal score at Study Day 8
Key Secondary	Time (days) to sustained recovery
Key Secondary	Sustained survival without respiratory failure (binary: 1=Yes or 0=No)
Secondary	Time (days) to at least 1 units improvement from baseline/Time (days) to at least 2 units improvement from baseline
Secondary	Difference from baseline ordinal score at Days 3, 5, 8, 11, 15, 22, 29
Secondary	Number of days ordinal score > 4
Secondary	Number of days ordinal score > 5
Secondary	Number of days ordinal score > 6
Secondary	Number of days of hospitalization
Secondary	Value of CRP, ferritin, D-dimer, LDH, fibrinogen
Secondary (safety)	14-Day mortality, 28-Day mortality, 59-Day mortality (binary: 1=Yes or 0=No)
Secondary (safety)	Time (days) to death

Pseudocode:

Method 1: Obtain Adjusted P-values from Westfall-Young for Continuous and Binary Endpoints using observed data

```
proc multtest data=dataset perm stepboot n=100000 seed=1234;
  class trt;
  test mean (C1 C2 C3/uppertailed) ;
      test mean (C4 C5 ... Cx/lowertailed) ;
  test fisher(B1 B2 B3 B4/lowertailed);
  test fisher(B5 B6 ... Bx/uppertailed);
  contrast 'Trt vs Placebo' -1 1;
  ods output pValues=pvals;
run;
```

Where C1 C2 ... Cx is a list of all continuous covariates and C1 C2 ... Cx is the list of all binary covariates. The contrast should be updated as needed so that the placebo group is the reference. Note that the variables are grouped depending on the direction of the hypothesis test.

Method 2: Obtain Adjusted P-values using Hochberg method: Use raw p-values as input from the primary analysis for all the endpoints in [Table 9](#).

```
proc multtest data=rawpvalues hoc out=adj_pvals;
run;
```

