9.6. Clinical Laboratory Evaluations

Clinical safety laboratory AEs are collected Study Days 1, 3, 5, 8, and 11 (while hospitalized); and outpatient Study Days 15 and 29 (if attends in-person visit or still hospitalized). Parameters evaluated include WBC, differential, Hgb, PLT, creatinine, (and calculate an estimated glomerular filtration rate (eGFR); the formula used is determined by the sites, but should be consistent throughout the study), total bilirubin, AST, ALT, and INR. Additional laboratory parameters may be summarized based on each intervention's safety profile. Laboratory safety parameters will be graded according to the NIAID Division of AIDS (DAIDS) Table for Grading the Severity of Adult and Pediatric Adverse Events, Corrected Version 2.1 (July 2017).

The distribution of Grade 3 and 4 chemistry and hematology laboratory results by maximum severity, time point, ordinal score and treatment group will be presented in [Table 62](#) through [Table 66](#) for chemistry and [Table 76](#) through [Table 81](#) for hematology. Absolute values and change from baseline of laboratory values will be summarized by mean, SD, median, minimum, and maximum results at Study Days 1, 3, 5, 8, 11, 15 and 29 in [Table 57](#), through [Table 61](#) for chemistry and [Table 67](#) through [Table 75](#) for hematology. Individual laboratory results are provided in [Listing 27](#) for chemistry and hematology and [Listing 29](#) for urine pregnancy results.

Markers of inflammation and coagulation results for CRP, ferritin, d-dimer, LDH, and fibrinogen will be summarized by mean, SD, median, minimum, and maximum results at Study Day 1 and Study Visit (not necessarily actual) Study Days 3, 5, 8, 11, 15 and 29 by treatment as well as change from baseline at each post-Study Day 1 visit ([Table 82](#)). Figures with mean and SD over time will also be presented by treatment ([Figure 31](#), [Figure 32](#), [Figure 33](#), [Figure 34](#), [Figure 35](#)). Individual results for markers of inflammation are presented in [Listing 28](#).

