N=Number of subjects in the Safety population. n= Number of unique subjects that satisfies the row criteria.									
^a Severity as per NIAID Division of AIDS (DAIDS) Table for Grading the Severity of Adult and Pediatric Adverse Events, Corrected Version 2.1 (July 2017).									

Tables with similar format:

Table 77: Platelets Results by Baseline Ordinal Score, Severity and Study Days — Safety Population

Table 78: Hemoglobin Results by Baseline Ordinal Score, Severity and Study Days — Safety Population

Table 79: INR Results by Baseline Ordinal Score, Severity and Study Days — Safety Population

Table 80: Neutrophils Results by Baseline Ordinal Score, Severity and Study Days — Safety Population

Table 81: Lymphocytes Results by Baseline Ordinal Score, Severity and Study Days — Safety Population

Table 82: Summary of Continuous Markers of Inflammation and Immune Response by Study Day — Safety Population

Study Day	Immune Response Measure	Treatment A (N=X)						Treatment B (N=X)					P-value ^a
		n	Mean	SD	Median	Min	Max	Mean	SD	Median	Min	Max	
Day 3	C-reactive protein	xx	x.x	x.xx	x.x	x	x	x.x	x.xx	x.x	x	x	0.xxx
	Ferritin	xx	x.x	x.xx	x.x	x	x	x.x	x.xx	x.x	x	x	0.xxx
	D-Dimer	xx	x.x	x.xx	x.x	x	x	x.x	x.xx	x.x	x	x	0.xxx
	Fibrinogen	xx	x.x	x.xx	x.x	x	x	x.x	x.xx	x.x	x	x	0.xxx
	LDH	xx	x.x	x.xx	x.x	x	x	x.x	x.xx	x.x	x	x	0.xxx
Rows should be repeated for Study Days 1, 5, 8, 11, 15, and 29													

SD= Standard Deviation. Min= Minimum. Max= Maximum. N=Number of subjects in Safety population.
 Values of D-Dimer reported as <220 were analyzed as 219 and values of CRP reported as <3.0 were analyzed as 2.9.
^a P-value of tests of two sample means.

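### Table 82 tests the inflammation and coagulation markers on unadjusted raw means and leaves out the Day 1 value already collected, which costs precision but not validity

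*SAP*

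**What the plan says.** - SAP Appendix 1, Table 82, has one p-value column for the five markers. Footnote a defines it as "P-value of tests of two sample means". The footnote does not say whether variances are pooled.
- The Table 82 shell carries the instruction "Rows should be repeated for Study Days 1, 5, 8, 11, 15, and 29", so the p-value is also printed for Day 1, before dosing.
- The only value handling given there is "Values of D-Dimer reported as <220 were analyzed as 219 and values of CRP reported as <3.0 were analyzed as 2.9". No log transformation or rank test appears, so I read the test as one on original units.
- SAP Table 6 (Section 6.4.3), other secondary safety endpoint 1, covers "Values of CRP ferritin, D-dimer, LDH, and fibrinogen on Study Day 1: Study Days 3, 5, 8, 11,15 and 29" and specifies "No covariate adjustment".
- SAP Section 9.6 says Table 82 will summarise the markers by treatment "as well as change from baseline at each post-Study Day 1 visit". The shell has no change columns, although the laboratory shells in Tables 57 and 67 do.
- SAP Table 9 (Section 6.8) also lists "Value of CRP, ferritin, D-dimer, LDH, fibrinogen" among the endpoints for the multiplicity and global analyses in Tables 44 and 45. Section 6.8 makes these optional.
- SAP Table 7 (Section 6.5.1) fills a missing baseline marker with another pre-treatment value or, failing that, with the earliest post-treatment value.

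**The concern.** Protocol Table 3 names CRP, ferritin, D-dimer and fibrinogen as a secondary efficacy measure, sampled on Day 1 and at later visits; the SAP adds LDH. The trial's rationale is to damp inflammation, and SAP Section 4.1 describes a proof-of-concept study that informs larger trials. A real marker effect that the test fails to show would be a loss for that purpose.

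A subject's own pre-dose value is usually among the best predictors of the later value, and the planned test does not use it. The SAP already adjusts for baseline CRP in survival without respiratory failure and in time to ventilation or death (Section 6.4.2), and uses it in the imputation model (Section 6.5.2), but not when the outcome is CRP itself. If a marker is also right-skewed, a few extreme subjects dominate a raw mean. Randomisation is stratified by site and ordinal score, not by any marker, so part of any chance imbalance at Day 1 carries into later visits.

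**Working it through.** **Which tests exist.** Table 82 is the only marker test not labelled optional. The Westfall-Young code for Table 44 uses lines such as "test mean (C4 C5 ... Cx/lowertailed", a one-tailed test of means with treatment as the only class variable. The global test in Table 45 takes z-scores from a linear model whose covariates are not listed, and Table 6 gives none for the markers. So no marker test is specified as using the Day 1 value.

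**Inputs from the documents.** There are 100 subjects per arm (SAP Section 5). Samples through Day 11 are taken only while hospitalised, and SAP Table 4 expects 34.6% of controls to be discharged by Day 8, which leaves 100 × (1 − 0.346) ≈ 65 per arm. I show 60 and 100, because the Table 7 imputation may raise the analysed number.

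**Assumed inputs.** Marker SD, baseline correlation ρ and effect are not stated. No significance level is set for the markers; I use two-sided 0.05. There is no marker power figure in the plan to reproduce.

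**Step 1: baseline adjustment alone.** Adjustment shrinks the SD by √(1 − ρ²), so power ≈ Φ(d√(n/2)/√(1 − ρ²) − 1.96). With d = 0.3 and n = 100, d√(n/2) = 2.121.
- Unadjusted: Φ(2.121 − 1.96) = Φ(0.161) = 56.4%.
- ρ = 0.3: 60.4%, so the unadjusted test loses 7% in relative terms.
- ρ = 0.5: 2.121/0.866 = 2.449, Φ(0.489) = 68.8%, loss 18%.
- ρ = 0.6: 75.5%, loss 25%.
- ρ = 0.7: 84.4%, loss 33%.

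**Step 2: baseline and log scale together.** Simulation: log marker at Day 1 and at follow-up bivariate normal with common SD and correlation ρ; active arm shifted by ln(0.65) at follow-up. The planned test is a Welch t-test on raw values. The comparator is ANCOVA of the log value on arm and log baseline. Loss = 1 − raw power / ANCOVA power.

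| Per arm | Log-SD | Raw test | Log ANCOVA, ρ = 0.3 / 0.5 / 0.7 | Relative loss |
|---|---|---|---|---|
| 60 | 0.8 | 71–72% | 86 / 92 / 98% | about 18–28% |
| 60 | 1.1 | 36–38% | 60 / 68 / 84% | about 40–56% |
| 100 | 0.8 | 90% | 98–100% | about 8–11% |
| 100 | 1.1 | 55–56% | 83 / 89 / 97% | about 33–44% |
| 60 or 100 | 0.4 | near 100% | near 100% | none |

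For example, 1 − 36/60 = 40% and 1 − 71/98 = 28%. Powers are rounded, and repeat runs move a loss by a point or two.

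**Step 3: smaller effects.** The 35% effect saturates both tests at log-SD 0.4. If the effect is instead sized so that log ANCOVA has about 80% power, with 100 per arm and ρ from 0.3 to 0.7, the loss is 8–39% at log-SD 0.4, 17–47% at 0.7, 30–55% at 1.0 and 44–63% at 1.3. Both components matter: at log-SD 1.0 and ρ = 0.5, power is 48% for the raw test, 55% for raw ANCOVA, 68% for the log t-test and 80% for log ANCOVA.

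**Step 4: validity.** With no treatment effect, the raw test rejected in 4.5% of simulated trials at nominal 5%.

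**The case against.** The strongest reply is that nothing depends on these p-values. Futility, early efficacy and the promising label all rest on the primary endpoint, and the markers are one item among many other secondary endpoints. That stands, and it limits the point to efficiency.

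A reader might infer more than the documents support:
- *That Table 82 is the only marker test.* Tables 44 and 45 also test these markers, though optionally and without a stated baseline adjustment.
- *That a third or more of the power is lost.* At 0.05 and a 35% effect this holds at log-SD 1.1 but not at 0.8. At two-sided 0.20, the SAP's threshold for a promising result, the loss with 60 per arm is about 6–12% at log-SD 0.8 and 20–30% at 1.1.
- *That the test is biased.* Only the correlated part of a baseline imbalance carries forward, and the unadjusted standard error already allows for it.
- *That the trial's pathway markers are affected.* IL-17A, IL-22 and IL-1b are exploratory, and SAP Section 3.2 leaves proteomic analysis to an addendum. Section 8.3 also defers markers of inflammation and immune response to a separate SAP, but Section 9.6 and Table 82 still analyse the five markers here.

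Baseline and skew are not wholly ignored: Section 9.6 promises descriptive change from baseline, and Table 82 prints median, minimum and maximum. Neither enters the test. The simulation assumes lognormal markers and does not model the Table 7 imputation; fibrinogen or LDH may be less skewed than CRP, ferritin or D-dimer.

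**Conclusion.** The point holds as one of precision. The planned test discards a pre-dose measurement that the trial already collects, and it works on raw means. The loss may be negligible or more than half of the power: for a 35% lower geometric mean at two-sided 0.05 it is nil at log-SD 0.4, moderate at 0.8 and large at 1.1, as tabulated. These figures rest on assumed SD, correlation and effect, so no single number should be quoted as the cost. Two shell defects stand without any power argument: the Day 1 p-value tests a difference that can only be chance between randomised arms, and the change-from-baseline summary promised in Section 9.6 has no place in Table 82. The change is worth making because it is cheap, not because any main conclusion is at risk.

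**What to change.** - In Table 82 and Table 6 (other secondary safety, row 1), replace the two-sample test with ANCOVA of log(marker) at each post-baseline visit on arm, log(Day 1 marker), actual baseline ordinal score and baseline steroid use. The last two are already the primary-endpoint covariates.
- Report the geometric mean ratio with 80% and 95% confidence intervals. Keep the raw descriptive columns, since the ratio answers a different question from a difference in arithmetic means.
- Allow only pre-dose values as the baseline covariate. For this analysis, override the Table 7 rule that lets the earliest post-treatment value stand in; otherwise the model could adjust for something treatment has already changed.
- Drop the Day 1 p-value and add the change-from-baseline columns.

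Cost: SAP wording, a revised shell and a little code, with no new data. The downside is that subjects with no pre-dose marker value do not contribute to the adjusted test.

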14.3.6 Displays of Vital Signs

Table 83: Summary Statistics of Baseline Vital Signs by Actual Baseline Ordinal Score and Treatment Group — Safety Population

Variable	Statistic	Treatment A (N=X)				Treatment B (N=X)				All Subjects (N=X)			
		BOS 5 (N=X)	BOS 6 (N=X)	BOS 7 (N=X)	Any BOS ^a (N=X)	BOS 5 (N=X)	BOS 6 (N=X)	BOS 7 (N=X)	Any BOS ^a (N=X)	BOS 5 (N=X)	BOS 6 (N=X)	BOS 7 (N=X)	Any BOS ^a (N=X)
Pulse	n	x	x	x	x	x	x	x	x	x	x	x	x
	Mean	x	x	x	x	x	x	x	x	x	x	x	x
	Standard Deviation	x	x	x	x	x	x	x	x	x	x	x	x
	Median	x	x	x	x	x	x	x	x	x	x	x	x
	Minimum	x	x	x	x	x	x	x	x	x	x	x	x
	Maximum	x	x	x	x	x	x	x	x	x	x	x	x
Diastolic Blood Pressure	n	x	x	x	x	x	x	x	x	x	x	x	x
	Mean	x	x	x	x	x	x	x	x	x	x	x	x
	Standard Deviation	x	x	x	x	x	x	x	x	x	x	x	x
	Median	x	x	x	x	x	x	x	x	x	x	x	x
	Minimum	x	x	x	x	x	x	x	x	x	x	x	x
	Maximum	x	x	x	x	x	x	x	x	x	x	x	x
Respiratory Rate	n	x	x	x	x	x	x	x	x	x	x	x	x
	Mean	x	x	x	x	x	x	x	x	x	x	x	x
	Standard Deviation	x	x	x	x	x	x	x	x	x	x	x	x
	Median	x	x	x	x	x	x	x	x	x	x	x	x
	Minimum	x	x	x	x	x	x	x	x	x	x	x	x
	Maximum	x	x	x	x	x	x	x	x	x	x	x	x
Blood oxygen Saturation	n	x	x	x	x	x	x	x	x	x	x	x	x
	Mean	x	x	x	x	x	x	x	x	x	x	x	x
	Standard Deviation	x	x	x	x	x	x	x	x	x	x	x	x
	Median	x	x	x	x	x	x	x	x	x	x	x	x
	Minimum	x	x	x	x	x	x	x	x	x	x	x	x
	Maximum	x	x	x	x	x	x	x	x	x	x	x	x

Variable	Statistic	Treatment A (N=X)				Treatment B (N=X)				All Subjects (N=X)			
		BOS 5 (N=X)	BOS 6 (N=X)	BOS 7 (N=X)	Any BOS ^a (N=X)	BOS 5 (N=X)	BOS 6 (N=X)	BOS 7 (N=X)	Any BOS ^a (N=X)	BOS 5 (N=X)	BOS 6 (N=X)	BOS 7 (N=X)	Any BOS ^a (N=X)
Oral Temperature	n	x	x	x	x	x	x	x	x	x	x	x	x
	Mean	x	x	x	x	x	x	x	x	x	x	x	x
	Standard Deviation	x	x	x	x	x	x	x	x	x	x	x	x
	Minimum	x	x	x	x	x	x	x	x	x	x	x	x
	Maximum	x	x	x	x	x	x	x	x	x	x	x	x

N=Number of subjects in the Safety population. n=number of subjects with a non-missing assessment.
^a There were X additional subjects with an Actual Baseline Ordinal Score of 4 that are included in the 'Any BOS' summaries.

14.4 Summary of Concomitant Medications

Table 84: Number and Percentage of Subjects with Prior Medications by WHO Drug Classification, Actual Baseline Ordinal Score, and Treatment Group — Safety Population

WHO Drug Code Level 1, Anatomic Group	WHO Drug Code Level 2, Therapeutic Subgroup	Treatment A (N=X)								Treatment B (N=X)								All Subjects (N=X)							
		BOS 5 (N=X)		BOS 6 (N=X)		BOS 7 (N=X)		Any BOS ^a (N=X)		BOS 5 (N=X)		BOS 6 (N=X)		BOS 7 (N=X)		Any BOS ^a (N=X)		BOS 5 (N=X)		BOS 6 (N=X)		BOS 7 (N=X)		Any BOS ^a (N=X)	
		n	%	n	%	n	%	n	%	n	%	n	%	n	%	n	%	n	%	n	%	n	%	n	%
Any Level 1 Codes	Any Level 2 Codes	x	xx	x	xx	x	xx	x	xx	x	xx	x	xx	x	xx	x	xx	x	xx	x	xx	x	xx	x	xx
ATC 1	Any ATC 2	x	xx	x	xx	x	xx	x	xx	x	xx	x	xx	x	xx	x	xx	x	xx	x	xx	x	xx	x	xx
	ATC 2	x	xx	x	xx	x	xx	x	xx	x	xx	x	xx	x	xx	x	xx	x	xx	x	xx	x	xx	x	xx
	ATC 2	x	xx	x	xx	x	xx	x	xx	x	xx	x	xx	x	xx	x	xx	x	xx	x	xx	x	xx	x	xx
ATC 1	Any ATC 2	x	xx	x	xx	x	xx	x	xx	x	xx	x	xx	x	xx	x	xx	x	xx	x	xx	x	xx	x	xx
	ATC 2	x	xx	x	xx	x	xx	x	xx	x	xx	x	xx	x	xx	x	xx	x	xx	x	xx	x	xx	x	xx
	ATC 2	x	xx	x	xx	x	xx	x	xx	x	xx	x	xx	x	xx	x	xx	x	xx	x	xx	x	xx	x	xx

Prior medications are defined as any medications begun before a subject took the first dose of study product. Medications are coded using the WHO Drug Dictionary version 202003.

ATC=Anatomical Therapeutic Chemical.

BOS= Baseline Ordinal Score.

N=Number of subjects in the Safety population.

n= Number of subjects reporting taking at least one medication in the specific ATC Class.

^a There were X additional subjects with an Actual Baseline Ordinal Score of 4 that are included in the ‘Any BOS’ summaries.

Table with similar format:

Table 85: Number and Percentage of Subjects with Concomitant Medications by WHO Drug Classification, Actual Baseline Ordinal Score, and Treatment Group — Safety Population

[Implementation note: Update the footnote to state ‘Concomitant medications are defined as any medications that begun after a subject took the first dose of study product or that begun before the first dose and continued after the subject took the first dose of study product.’]

Table 86: Summary of Concomitant COVID-19 Treatments — Safety Population

Type	Summary Measure	Treatment A (N=X)						Treatment B (N=X)					
		n	Mean	SD	Median	Min	Max	n	Mean	SD	Median	Min	Max
[COVID-19 Treatment 1]	Number of Subjects	x	-	-	-	-		x	-	-	-	-	-
	Study Day Onset ^a	x	x.x	x.xx	x.x	x	x	x	x.x	x.xx	x.x	x	x
	Duration (days)	x	x.x	x.xx	x.x	x	x	x	x.x	x.xx	x.x	x	x

Concomitant COVID-19 Treatments are defined as medications that started before dose 1 of study product and continued throughout the study or those started after a subject took study product.

SD=Standard Deviation. Min=Minimum. Max=Maximum.

N=Number of subjects in the Safety population.

n=Number of subjects reporting at least one of the concomitant COVID-19 treatments. Refer to Section 6.4 for a list of COVID-19 treatments of interest.

^a Study day onset is defined as the start day of the concomitant medication.

Table 87: Summary of Steroid Usage for Indications Other than COVID-19 by Treatment of Indication — Safety Population

Type	Summary Measure	Treatment A (N=X)						Treatment B (N=X)					
		n	Mean	SD	Median	Min	Max	n	Mean	SD	Median	Min	Max
[COVID-19 Treatment 1]	Number of Subjects	x	-	-	-	-		x	-	-	-	-	-
	Study Day Onset ^a	x	x.x	x.xx	x.x	x	x	x	x.x	x.xx	x.x	x	x
	Duration (days)	x	x.x	x.xx	x.x	x	x	x	x.x	x.xx	x.x	x	x

Concomitant Steroid Treatments are defined as steroids for indications other than COVID-19 that started before dose 1 of study product and continued throughout the study or those started after a subject took study product.
SD=Standard Deviation. Min=Minimum. Max=Maximum.
N=Number of subjects in the Safety population.
n=Number of subjects reporting steroid usage for indications other than COVID-19. Refer to Section 6.4 for a list of steroids of interest.
^a Study day onset is defined as the start day of the concomitant medication.

